7.1 Allowed Medications and Treatments

Standard therapy for asthma is allowed except for treatments noted in the exclusion criteria described above and as noted in the prohibited medications section below.

7.2 Prohibited Medications and Treatments

The following medications are prohibited during the study and administration will be considered a protocol violation.

- Thiols and thiol derivatives
- Activated charcoal
- Inhaled insulin

8 STUDY TREATMENTS

8.1 Method of Assigning Subjects to Treatment Groups

There is one treatment group all subjects will be assigned to.

8.2 Blinding

Due to the objectives of the study, the identity of test and control treatments will be known to investigators, research staff, and patients. Study treatments will not be blinded.

8.3 Formulation of Test and Control Products

NAC (trade name: Mucomyst) is manufactured by American Regent. The active drug studied here is 20% NAC. It will be delivered via nebulizer.

8.3.1 Formulation of Test Product

20% NAC is an existing formulation of Mucomyst (Mucomyst-20), manufactured by American Regent, for aerosol administration in the management of patients with chronic bronchopulmonary disease. 20% NAC is a colorless solution that requires no reconstitution.

Albuterol sulfate inhalation solution is an existing formulation of Proventil Nebules, manufactured by Nephron Pharmaceuticals Corporation for oral inhalation in the management of patients with bronchospasm. Albuterol sulfate inhalation solution is a clear, colorless solution.

Table 1: Formulation and Measured pH of 20% NAC and albuterol

| | 20% NAC | Albuterol |
|--------------------------|---|--|
| Active Ingredient, mg/mL | Acetylcysteine 200mg/mL | Albuterol sulfate 0.83mg/mL |
| Other ingredient, mg/mL | Edetate disodium, sodium hydroxide, purified water | Water, sodium chloride, sulfuric acid |
| pH | 7 | 3-5 |

8.3.2 Packaging and Labeling

The test product will be in its original packaging and is provided by the UCSF Pharmacy. It will be ordered as a medication through the patient's electronic medical record (EMR).

8.4 Supply of Study Drug at the Site

The UCSF Pharmacy will order the study drug and albuterol per the patient's medication administration record (MAR). It will be located in the Pyxis MedStation on the medical-surgical ward the patient is admitted on.

8.4.1 Dosage/Dosage Regimen

During each treatment, participants will receive a mixture of 3 mL of study drug and .5 mL of albuterol. It will be delivered via nebulizer. Subjects will take four treatments a day, spaced at approximately 4 - 6 hour intervals. The treatment period is five days. No adjustments will be made based on weight or age.

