| 
SUBJECT SELECTION CRITERIA
 | 
Inclusion Criteria
 
 1. Male or female between the ages of 18 and 80 years of age at Visit 1 2. Written informed consent obtained from subject and ability for subject to comply with the requirements of the study. 3. Able to perform reproducible spirometry according to ATS criteria 4. Physiological evidence of airflow obstruction (FEV1 bronchodilator reversibility of $\geq 12\%$ or hyperreactivity to methacholine reflected by a methacholine PC20 ≤ 16 mg/mL) 5. Clinical history of asthma per patient report or medical record 6. Pre-bronchodilator FEV1 $> 35\%$ predicted 7. Post-bronchodilator FEV1 $> 40\%$ but $< 90\%$ predicted 8. Asthma requiring treatment with inhaled corticosteroids (ICS) for 3 months or greater 9. CT mucus score ≥ 5 
Exclusion Criteria
 
 1. Pregnant, breastfeeding, or unwilling to practice birth control during participation in the study. 2. Presence of a condition or abnormality that in the opinion of the Investigator would compromise the safety of the patient or the quality of the data. 3. Smoking of tobacco or other recreational inhalants in last year and/or > 10 pack-year smoking history 4. Current participation in an investigational drug trial 5. Other chronic pulmonary disorders, including (but not limited to) cystic fibrosis, chronic obstructive pulmonary disease, chronic bronchitis, vocal cord dysfunction (that is the sole cause of respiratory symptoms and at the PI's discretion), severe scoliosis or chest wall deformities that affect lung function, or congenital disorders of the lungs or airways 6. Unwillingness to follow study procedures 7. History of allergy or intolerance to study drug 8. Any other criteria that places the subject at unnecessary risk according to the judgment of the Principal Investigator |
| 
TEST PRODUCT, DOSE, AND ROUTE OF ADMINISTRATION
 | 
20% NAC (3 mL) and albuterol (.5 mL) Product will be administered every 4-6 hours for 5 days during an inpatient stay at the hospital. Medication will be delivered by inhalation via nebulizer.
 |
| 
CONTROL PRODUCT, DOSE
 | 
No control product
 |

| | |
|--|--|
| AND ROUTE OF ADMINISTRATION | |

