2.1 Risk / Benefit Assessment

Risk: Inhaled n-acetylcysteine (NAC) is approved for the treatment of mucus associated airway disease, including asthma. The main side effect from inhaled n-acetylcysteine (NAC) is bronchospasm. We find that co-administering NAC and albuterol effectively prevents excessive bronchoconstriction in asthmatic patients. Specifically, in ten asthmatics that were given doses of 20% NAC as high as 3 mL together with 3 mL of albuterol, the largest FEV1 decline was 6%.

Benefit: Mucus plugs cause airway obstruction and symptoms of dyspnea. The role of mucolytics in decreasing plugs and increasing FEV1 has not been well studied. Our preliminary data, utilizing CT imaging and a novel scoring system, can identify and target a subgroup of patients who may benefit from inhaled mucolytic treatment more so than the asthmatic population as a whole.

To minimize risk, study participants will be admitted to a medical-surgical ward in the hospital and given all treatments under the supervision of a registered nurse and the covering medical team. Our study team of experienced clinicians will be available as needed.

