8.4.3 Administration Instructions

3 mL of study drug and .5 mL of albuterol sulfate should be carefully added to the nebulizer.

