10.5 Visit 4 (Day 1)

1. Record changes to concomitant medications.
2. Perform and record vital signs.
3. Perform and record oximetry.
4. Perform and record fractional exhaled nitric oxide (FeNO) measurement.
5. Perform and record spirometry.
6. Perform and record 3 peak flow AM measurements before first treatment of the day.
7. Perform and record post-bronchodilator reversibility.
8. Admit patient to medical-surgical floor.
9. Administer study drug treatment three times over the course of the day, spaced every 4-6 hours. Peak flow measurements should be taken before and after each treatment.
10. Perform and record 3 peak flow PM measurements after all treatments have been completed.

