10.6 Visit 5 (Day 2)

1. Perform and record fractional exhaled nitric oxide (FeNO) measurement.
2. Perform and record spirometry.
3. Perform and record 3 peak flow AM measurements before first treatment of the day.
4. Administer study drug treatment four times over the course of the day, spaced every 4-6 hours. Perform peak flow measurements before and after each treatment.
5. Perform and record 3 peak flow PM measurements after all treatments have been completed.

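### The regimen gives 0.5 mL of albuterol per treatment, but the safety evidence in section 2.1 used 3 mL, and the sixfold gap is not explained

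*Protocol*

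**What the plan says.** Three places in the protocol set the dose, and they agree. Section 8.4.1 states that "participants will receive a mixture of 3 mL of study drug and .5 mL of albuterol". The synopsis lists the test product as "20% NAC (3 mL) and albuterol (.5 mL"), and the instruction in 8.4.3 is that "3 mL of study drug and .5 mL of albuterol sulfate should be carefully added to the nebulizer".

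The only albuterol strength in either document is in Table 1 of section 8.3.1: "Albuterol sulfate 0.83mg/mL". No dose in mg per treatment appears anywhere.

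Section 2.1 names bronchospasm as the main side effect of inhaled NAC and puts forward albuterol as the protection: "We find that co-administering NAC and albuterol effectively prevents excessive bronchoconstriction in asthmatic patients". The evidence offered is ten asthmatics "given doses of 20% NAC as high as 3 mL together with 3 mL of albuterol, the largest FEV1 decline was 6" per cent. The strength of that albuterol is not given.

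On frequency, the Day 1 visit list (10.5) says "Administer study drug treatment three times over the course of the day, spaced every 4-6 hours". The lists for Days 2 to 5 (10.6 to 10.9) say "Administer study drug treatment four times over the course of the day, spaced every 4-6 hours".

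**The concern.** The NAC volume in the trial equals the maximum in the cited experience, but the albuterol volume is one sixth of it. The protocol neither acknowledges nor explains this. It names no concentrated albuterol solution and gives no safety data at 0.5 mL.

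Albuterol is the agent the protocol relies on to prevent its main named risk. Patients can enter with a pre-bronchodilator FEV1 just above 35% predicted (6.2). Nurses take the drug from a ward cabinet (8.4.2) and are told a volume, not a dose in mg. If the cabinet holds the solution in Table 1, exact compliance delivers 0.415 mg each time. If both solutions had the same strength, the ten-patient result says nothing direct about that dose.

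**Working it through.** **Inputs.** Trial albuterol volume 0.5 mL (synopsis, 8.4.1, 8.4.3). Albuterol strength 0.83 mg/mL (Table 1). Cited albuterol volume 3 mL, strength not stated (2.1). NAC 3 mL in the trial and up to 3 mL in the cited experience. The plan states no mg dose, so there is no figure of its own to reproduce.

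**Dose = volume × strength**

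- Trial as written: 0.5 × 0.83 = 0.415 mg per treatment.
- Cited experience, if the same solution was used: 3 × 0.83 = 2.49 mg.
- Volume ratio: 3 / 0.5 = 6.0. The mg ratio is also 6.0 at equal strength.

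**Strengths that would make the doses match, keeping both volumes**

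- Trial solution stronger: 2.49 / 0.5 = 4.98 mg/mL, about 5 mg/mL.
- Cited solution weaker: 0.415 / 3 ≈ 0.14 mg/mL.

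Neither strength is in the documents; both are back-solved.

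**Readings**

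| Reading | Trial dose | Cited dose | Ratio |
|---|---|---|---|
| Both volumes right, same solution | 0.415 mg | 2.49 mg | 6.0 |
| Trial solution about 5 mg/mL (assumed), cited solution 0.83 mg/mL | about 2.5 mg | 2.49 mg | 1.0 |
| Trial solution 0.83 mg/mL, cited solution about 0.14 mg/mL (assumed) | 0.415 mg | about 0.415 mg | 1.0 |
| Volume slip in 2.1 (3 mL should be 0.5 mL), same solution | 0.415 mg | 0.415 mg | 1.0 |
| Volume slip in the dosing text (0.5 mL should be 3 mL), same solution | 2.49 mg | 2.49 mg | 1.0 |

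The table does not bound the mg ratio. A cited solution stronger than 0.83 mg/mL, with the trial at 0.415 mg, would put it above 6.

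**Exposure.** By the visit lists, 3 + 4 × 4 = 19 treatments per patient, and 30 × 19 = 570 in total. Section 8.4.1 read literally (four a day for five days) gives 20 and 600. The per-treatment question is the same either way.

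**The case against.** The strongest reply is that only the volume difference is certain. Section 2.1 gives no strength, several plausible readings bring the mg ratio to 1.0, and nothing shows that 0.5 mL is inadequate. The ten-patient data compare no albuterol doses, so they do not show that 3 mL is needed either. All of this stands. It limits the claim to an unreconciled dose, and does not support saying that patients are under-protected.

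The second reply is that other protections exist: supervised inpatient dosing (2.1), peak flow before and after each treatment (5.3), continued asthma therapy (7, 7.1), exclusion for intolerance to study drug (6.3), stopping for an adverse event (12.1), and pharmacy ordering through the medication record (8.4), where the ambiguity could surface. Section 2.1 also cites approved use in asthma. On Day 1 the reversibility test, with four to eight puffs of albuterol (9.1.10), is listed before the first study treatment.

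These limit the harm but do not resolve the discrepancy. Supervision and peak flow mainly detect bronchospasm after it starts, and neither 5.3 nor the inpatient visit lists state a peak-flow fall that triggers rescue or stopping. Sputum induction, by contrast, has calculated 10% and 20% falls and a discharge rule (9.1.12). The Day 1 reversibility test is not repeated on Days 2 to 5. The pharmacy might catch the problem, but the protocol does not ask it to. None of this shows that 0.415 mg prevents bronchospasm.

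The suggestion that a concentrate was probably meant does not help either: in that case Table 1 does not describe the product in use.

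**Conclusion.** The concern holds and should be fixed. The albuterol volume differs by a factor of 6.0 between the regimen and the evidence cited for its safety, and no text in the protocol or SAP accounts for it. The trial dose as written, at Table 1's strength, is 0.415 mg per treatment. The corresponding 2.49 mg for the cited experience, and hence a sixfold ratio in mg, assumes that the ten patients received the same solution.

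The documents cannot settle whether the dose is truly lower, a strength is wrong or missing, or a volume is misstated. Under every reading, a volume, a strength or the claim in 2.1 has to be corrected or clarified. Confidence is high in the discrepancy; no claim is made that the lower volume causes harm.

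**What to change.** 1. Confirm the albuterol product, strength and volume with the pharmacy, and check the ten-patient albuterol volume and strength against the source data.
2. State the dose per treatment in mg in 8.4.1, with a volume and strength that multiply to it, and make the synopsis, Table 1 and 8.4.3 consistent with it. Suggested form: *3 mL of 20% NAC (600 mg) plus albuterol __ mg (__ mL of __ mg/mL)*. The 600 mg is 3 mL × 200 mg/mL from Table 1.
3. State the ten-patient experience in mg in 2.1, and correct whichever figure proves wrong.
4. If the trial dose really is lower, add to 2.1: *This result was obtained at a higher albuterol dose (__ mg) than the trial dose (__ mg) and does not show prevention at the trial dose.* Whether to raise the dose is then for the sponsor's clinical judgement.

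The cost is two record checks, wording changes in up to five places (2.1, synopsis, Table 1, 8.4.1, 8.4.3) and IRB approval. No patients, visits or tests are added. Only if 3 mL of albuterol is adopted does the nebulizer volume change, from 3 + 0.5 = 3.5 mL to 3 + 3 = 6 mL per treatment.

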8.4.2 Dispensing

Study medication will be dispensed from the Pyxis MedStation by the floor nurse.

8.4.3 Administration Instructions

3 mL of study drug and .5 mL of albuterol sulfate should be carefully added to the nebulizer.

8.4.4 Storage

Study drug supply will be maintained by the UCSF Pharmacy and will be supplied following hospital pharmacy regulations according to the stocking and storage of the Pyxis Medstation.

Study drug should be stored by the study site pharmacy at controlled room temperature, 15 to 30°C (59 to 86°F). If the temperature of study drug storage in the pharmacy exceeds or falls below this range, this should be reported to the Sponsor or designee and captured as a deviation. Subjects and study staff will be instructed to store the medication in original packaging at room temperature according to the instructions outlined on the Drug Administration Instructions until ready for administration.

8.5 Study Drug Accountability

An accurate and current accounting of the dispensing of study drug for each participant will be maintained on an ongoing basis by the study nurse or study site staff. The number of study drug dispensed will be recorded. The study monitor will verify these documents throughout the course of the study.

8.6 Measures of Treatment Compliance

Participants will be monitored by a nurse or study staff. The nurse administering the study treatment will record the date and time the study drug was administered as well as any adverse events on a study case report form. Study staff will verify these documents throughout the course of the study.

9 STUDY PROCEDURES AND GUIDELINES

A Schedule of Events representing the required testing procedures to be performed for the duration of the study is diagrammed in Appendix 1.

Prior to conducting any study-related activities, written informed consent and the Health Insurance Portability and Accountability Act (HIPAA) authorization must be signed and dated by the subject.

9.1 Clinical Assessments

9.1.1 Concomitant Medications

All concomitant medication and concurrent therapies will be documented at Visits 1-4 and at early termination when applicable. Dose, route, unit frequency of administration, and indication for administration and dates of medication will be captured.

9.1.2 Medication Withholding

Maximum bronchodilator reversibility will be used to establish eligibility at Visit 2 and post-bronchodilator reversibility will be assessed at Visits 3, 4, 9, 10, 11. Since some asthma medications can blunt the response to bronchodilators, we will ask that participants withhold these medications according to the guidance provided in Table 2.

Table 2. Medication Withholding Parameters

| Medication | Withholding Period |
|---|--------------------|
| Leukotriene modifiers | 24 hrs |
| Ultra-long-acting bronchodilators (indacaterol, tiotropium) | 24 hrs |
| Long-acting beta-agonists | 12 hrs |
| Theophylline | 12 hrs |
| Short-acting anticholinergic | 6 hrs |
| Short-acting beta-agonists | 4 hrs |

Participants will be evaluated at Visit 1, without any medication holds, to establish the safety of withholding asthma medications. If a study clinician feels the participant is not clinically stable enough to withhold medications, they may shorten the guidance (with appropriate documentation on the Visit 1 CRF Physician Attestation section) or they may excuse the participant from some or all of the medication withholds.

Participants are reminded of these medication holds by phone 24 hours prior to their medication withholding visits and instructed to resume all medications should symptoms develop in the period prior to the visit.

Associated risks of medication withholding include a worsening of asthma control or asthma exacerbation. To mitigate these risks, participants are given clear instructions to resume asthma medications if symptoms arise.

9.1.3 Food and Beverage Withholding

Participants are asked to withhold eating for one hour prior to the sputum induction at visit 3 since recently digested food can contaminate sputum samples. Participants are also asked to withhold caffeine and alcohol-containing products for 6 hours prior to all study visits as these substances can influence lung function values.

9.1.4 Demographics

Demographic information (date of birth, gender, race) will be recorded at Visit 1.

9.1.5 Medical History

Relevant medical history, including history of current disease, other pertinent respiratory history, and information regarding underlying diseases will be recorded at Visit 1.

Associated risks include discomfort evoked with some of the questions asked. To minimize risk, participants will be informed that they can defer answering any questions that make them feel uncomfortable.

9.1.6 Physical Examination

A complete physical examination will be performed by either the investigator or a study clinician at Visit 1. Qualified staff (MD, NP, RN, and PA) may complete the abbreviated physical exam at all other visits. New abnormal physical exam findings must be documented and will be followed by a physician or other qualified staff at the next scheduled visit.

9.1.7 Vital Signs

Body temperature, blood pressure, pulse and respirations will be performed after resting for 5 minutes at all study visits.

9.1.8 Oximetry

Oximetry will be measured on room air with the subject at rest at all study visits at the Airway Clinical Research Center.

9.1.9 Spirometry

Spirometry will be performed at all study visits and in accordance with the current American Thoracic Society recommendations for the performance and interpretation of tests.

Associated risks include the following:

- Likely (>10%): Shortness of breath or cough during the six-second-exhalation
- Less Likely (<5%): Wheezing and chest tightness
- Rare but serious (<1%): Syncope

In an effort to minimize risk, participants will be seated during the procedure to reduce any injury should a participant become dizzy and fall. Study staff will have albuterol available to administer to participants who develop wheeze or shortness of breath following spirometry.

9.1.10 Post-Bronchodilator / Maximum Reversibility

Spirometry will be repeated 15 minutes following the administration of four to eight puffs of albuterol to assess bronchodilator reversibility. Maximal bronchodilation will be performed at Visit 2. Post-bronchodilator reversibility will be performed at Visit 3, 4, 9, 10, 11 and 12.

Associated risks include the following:

- Likely (>10%): Transient tachycardia, tremor, feeling nervous, rhinitis, pharyngitis, and nausea
- Less Likely (<5%): Headache, cough, upper respiratory infection

- Rare but serious (<1%): Chest pain, atrial fibrillation, hypertension, hypotension, diabetic ketoacidosis, hyperglycemia, hypersensitivity reactions, paradoxical bronchospasm

Given that the study population is made up of individuals with moderate-to-severe asthma, and that albuterol is a standard of care treatment for asthma, it is unlikely that participants will experience any of the side effects described above. However, if a potential participant describes previous sensitivity or side effects to treatment with albuterol, they will be excluded from participation for safety. Furthermore, albuterol will only be administered after a physician-administered history and physical, to ensure that it is okay for the participant to receive albuterol.

9.1.11 Methacholine Challenge Testing

Methacholine challenge testing is performed to assess airway responsiveness. Only participants that are unable to achieve $\geq 12\%$ improvement in FEV1 following administration of four to eight puffs of albuterol and who have a baseline FEV1 $> 50\%$ predicted will undergo methacholine challenge testing at Visit 2b. In the methacholine challenge test, increasing concentrations of methacholine are delivered until the FEV1 falls by 20% or more compared to the reference (post-diluent baseline) level. When the provocative concentration that causes a 20% fall (PC20) is identified, the challenge is stopped.

Associated risks include the following:

- Likely ($>10\%$): Shortness of breath
- Less Likely ($<5\%$): Wheezing, chest tightness, or cough
- Rare but serious ($<1\%$): Rarely, patients may have severe bronchoconstriction during or following methacholine challenge

Additionally, methacholine has been shown to increase tone of the uterus, which could lead to preterm labor, in pregnancy laboratory animals; there are no human studies to verify this effect during pregnancy. However, because of this, methacholine has been placed in FDA Category C, meaning that exposure during pregnancy should be avoided. As such, pregnant women or women of reproductive age who are unwilling to practice pregnancy prevention strategies will be excluded from participation.

In an effort to minimize risk to participants, only those participants with a pre-diluent FEV1 of $> 50\%$ predicted and at least one liter will undergo the methacholine challenge testing, and only in the instance that they are not able to show 12% or greater improvement in FEV1 following bronchodilator administration. A study physician will be available during the challenge. Participants will not be discharged until their FEV1 is within 10% of their pre-diluent FEV1. Medications and personnel will be available to manage and treat bronchoconstriction.

